1. PURPOSE OF THE STUDY

a. Brief Summary

This study aims to test the effectiveness of a Type 2 Diabetes (T2D) prevention program for individuals who have been diagnosed with prediabetes compared to a T2D educational control group. Project Health is an obesity prevention program and has produced a 42% to 53% reduction in future onset of overweight/obesity and also produced greater reductions in negative affect compared to assessment-only controls that persisted. Project Health has been adapted to prevent onset of T2D among individuals with prediabetes. The study aims to test the effectiveness of Project Health at reducing BMI, HbA1c levels, increase physical activity and improve glucose control.

b. Objectives

Aim 1 is to test the hypothesis that participants who complete the T2D Project Health will show significantly greater reductions in BMI and HbA1c, the primary outcomes, by 3-month follow-up than participants randomized to the T2D education video control condition.

Aim 2 is to test the hypothesis that participants who complete the T2D Project Health will show significantly greater reductions in self-reported caloric intake and greater increases in physical activity by 3-month follow-up than participants randomized to the T2D education video control condition.

If this pilot and feasibility trial provides evidence that Project Health significantly reduces weight gain and improves glucose control, we plan on conducting a fully-power trial that will test whether this brief, cost effective prevention program significantly reduces future onset of T2D among individuals with impaired glucose control. As such, this represents a translational study on the prevention of T2D.

c. Rationale for Research in Humans

The purpose of this study is to test the effectiveness of a Type 2 Diabetes prevention program, adapted Project Health. This study must use humans due to the nature of the educational aspect because the programs require speech as a method of communication.

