We will use a random number generator to determine if participants will be in Project Health or the educational control. If an even number is generated, the participant will be assigned Project Health. If an odd number is generated, the participant will be assigned to educational control. As there is a 50% chance the number will be either even or odd, there is a 50% chance that someone will be assigned either to Project Health or the educational control. It is only after the baseline assessment that individuals will be randomized. This will prevent the assessor at baseline from being influenced by which group the participant will be in. The assessor completing the assessments at post-test and 3-month follow-up will be blind to the participant's condition.

Project Health:

Project Health will be delivered in six 1-hour group sessions that will be held weekly. In addition, participants will be asked to complete 30 mins of response inhibition and attention trainings once per week between the sessions. This program promotes to retain the gradual lifestyle modification designed to bring energy intake into balance with energy output and the food response inhibition and attention training, but will adapt the dissonance-induction activities to focus on the negative

effects of developing T2D in addition to the negative effects of obesity, overeating, and a sedentary lifestyle.

Participants who are assigned to the Project Health condition will receive reminders and writing prompts via a secure text messaging platform, TextMagic. The text reminders will be used to remind participants to complete the writing prompts and one computer task between group sessions. This computer task is a choice of one game that the participants had played during their intervention group. The writing prompts being used will help to reinforce the response inhibition and attention trainings. No personal participant information will be shared or asked for via TextMagic.

Educational Control:

We selected a T2D management psychoeducational comparison condition. To match Project Health, the educational videos will be delivered in 6 1-hour blocks. The educational group will be instructed to watch videos on nutrition, exercise, and how to maintain general health during the lifespan

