Evaluating a Type 2 Diabetes Prevention Program

NCT: 5822648

04/16/2023

**Analyses.** For the continuous response variables in Aims 1 and 2 we will fit linear mixed effects models (LME) or generalized additive models (GAM) if change across the study is nonlinear. All models will include an interaction of time since the start of the study (in months) and condition (as well as all lower-order main effects). For both LMEs and GAMs, we will control for the lack of independence between the observations within a participant by including random intercepts and random slopes (if necessary) for the participants in our models and for participants nested within groups.

To detect for differences in the onset of T2D (Aim 1) between the intervention and control condition, we will fit a Cox proportional hazard model using the survival package (Therneau, 2022) in R. The proportional hazard assumption will be assessed and in the event of violations of this assumption, stratified proportional hazard models will be fit.

For the mediation analysis for Aim 2, the mediation package (Tingley et al., 2014) in R will be used to employ the causal mediation approach described in Imai et al. (2010). This is a more general and flexible causal mediation framework than the traditional structural equation modeling approach to mediation. Specifically, this approach enables (1) definitions of causal mediation effects that are independent of a particular statistical model, (2) specification of the identifiability assumption, and (3) a framework that can be applied to a myriad of models (most importantly for this study, LMEs, GAMs, and survival models). In addition, sensitivity analyses can be conducted to explore the sequential ignorability assumption. Using this framework involves modeling the onset of T2D via a parametric survival regression model that includes condition and the proposed mediator (percent body fat). This model's output is then combined with the mediator model's output, the percent body fat model from Aim 1, and used to calculate the average causal mediation effect (ACME), the proportion of the total effect that is mediated as well as other mediation statistics, which can then be tested using either quasi-Bayesian Monte Carlo or the non-parametric bootstrap.

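### The SAP's continuous-outcome models leave the arms' baseline means free to differ, which gives up HbA1c precision that baseline adjustment could recover

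*SAP*

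**What the plan says.** Protocol section 1b states the primary hypothesis as "significantly greater reductions in BMI and HbA1c, the primary outcomes, by 3-month follow-up". The SAP (Analyses) covers these outcomes as follows: "For the continuous response variables in Aims 1 and 2 we will fit linear mixed effects models (LME"), or generalized additive models (GAMs) if change is nonlinear. On the fixed effects it says "All models will include an interaction of time since the start of the study (in months) and condition", and it keeps the lower-order terms: "condition (as well as all lower-order main effects"). The random part is described as "including random intercepts and random slopes (if necessary) for the participants in our models", with nesting in groups. No baseline covariate and no common-baseline constraint is mentioned.

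On timing, protocol section 2a (Randomization) says "It is only after the baseline assessment that individuals will be randomized". Section 2a (Post-Test) leaves the blood tests out of post-test, which gives HbA1c two visits up to the 3-month follow-up. Section 8m lists HbA1c at post-test.

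Diabetes onset is handled separately: "we will fit a Cox proportional hazard model using the survival package". For mediation the SAP uses "a parametric survival regression model that includes condition and the proposed mediator (percent body fat").

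**The concern.** If time zero is the baseline visit, the condition main effect is the difference between arms at baseline. Randomisation comes after that visit, so the true difference is zero, and estimating it adds noise to the treatment contrast. In a given trial, the estimate also over-corrects any chance baseline imbalance. The even/odd draw in section 2a has no blocking or stratification to limit such imbalance. At stake is precision on a co-primary outcome in a 62-person pilot whose result decides whether a fully powered trial follows.

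**Working it through.** The plan gives no power calculation, so there is no figure of its own to reproduce.

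**Inputs from the documents.** N = 62 (protocol 8a), taken as 31 per arm; 1:1 allocation in expectation (2a); baseline before randomisation (2a); model terms (SAP, Analyses).

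**Assumptions.** Baseline to follow-up correlation rho of 0.5 to 0.8 for HbA1c and about 0.98 for BMI; equal SD at both visits; two-sided 5% test; no dropout; no group clustering.

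**Step 1: what the interaction estimates.** With two complete visits, the time-by-condition coefficient multiplied by the follow-up length is the difference between arms in mean change. Random-intercept models fitted to simulated two-visit data matched the change-score difference to about 1e-15.

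**Step 2: variances per participant, in units of SD².**
- Change score: 2(1 − rho)
- Baseline-adjusted: 1 − rho²
- Ratio: (1 − rho²) / [2(1 − rho)] = (1 + rho)/2

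The SE reduction is 1 − √ratio, and the equivalent sample size is 62/ratio. The last column is the power of the adjusted analysis at the difference for which the change score has 80% (normal approximation).

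| rho | change | adjusted | ratio | SE reduction | 62/ratio | power |
|---|---|---|---|---|---|---|
| 0.5 | 1.00 | 0.75 | 0.75 | 13% | 83 | 90% |
| 0.6 | 0.80 | 0.64 | 0.80 | 11% | 78 | 88% |
| 0.7 | 0.60 | 0.51 | 0.85 | 8% | 73 | 86% |
| 0.8 | 0.40 | 0.36 | 0.90 | 5% | 69 | 84% |
| 0.98 | 0.040 | 0.0396 | 0.99 | 0.5% | 63 | 80% |

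**Step 3: cost of estimating the slope.** The factor (N − 3)/(N − 4) = 59/58 = 1.017 moves the ratios to 0.76 (rho 0.5), 0.92 (rho 0.8) and 1.007 (rho 0.98). A simulation of 3,000 trials gave 0.82 at rho 0.6 and 1.00 at rho 0.98.

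**Step 4: three visits.** If HbA1c is also taken at post-test, the exact identity no longer holds. For a linear slope with visits at 0, 1.5 and 4.5 months and equal correlations between visits, the constrained-to-free variance ratio is 0.78 at rho 0.5, 0.83 at 0.6 and 0.92 at 0.8. Most of the gain remains.

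**Step 5: chance imbalance.** With equal SDs the change-score estimate shifts by (1 − rho) times the baseline imbalance. An imbalance of one SE is √(2/31) = 0.254 SD, so at rho 0.6 the shift is 0.4 × 0.254 = 0.10 SD.

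**Step 6: eligibility and HbA1c.** Without the equal-SD assumption, the ratio is R / [R + (1 − b)²·s0²], where R is the residual variance, b the slope on baseline and s0 the baseline SD. Take an unrestricted rho of 0.8 and SD 1, so R = 0.36 and b = 0.8.
- No restriction: 0.36/(0.36 + 0.04) = 0.90.
- Baseline value itself confined to a band one SD wide (s0² about 1/12 = 0.083): 0.36/(0.36 + 0.04 × 0.083) = 0.99, almost no gain. The observed correlation drops to about 0.35, and (1 + rho)/2 would wrongly give 0.67.
- A separate earlier test confined to that band: each visit has variance 0.36 + 0.64 × 0.083 = 0.413, and the covariance is 0.16 + 0.053 = 0.213. So rho = 0.52 and the ratio is about 0.76.

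**The case against.** The strongest reply is that nothing here is invalid. The change contrast is unbiased over randomisation, its simulated type I error is 5.0% (rho 0.6), and it directly answers a hypothesis about reductions. That stands. Baseline is used, with its coefficient fixed at 1, so a reader who infers that it is discarded, or that the estimate is biased on average, goes too far.

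Three other stronger readings are tempting, and the documents do not support them.
- **All outcome models are affected.** The Cox model and the parametric survival model for diabetes onset have no repeated baseline measure of the outcome. The point is confined to the LMEs and GAMs.
- **A narrow eligibility band makes HbA1c the main loser.** Step 6 shows that this reverses if the baseline value itself is restricted. Section 2a puts the baseline assessment after eligibility is confirmed, which favours a separate test, but no section says which test decides. Section 8h also admits participants on fasting glucose alone, which does not bound HbA1c.
- **Deleting the condition term is a sufficient fix.** The SAP does not define the start of its time scale, and in a GAM with centred smooths the deletion does not impose equal baseline means.

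The size also rests on no dropout and no clustering. Project Health runs in groups of 6, and group-level variance arising after baseline is not removed by adjustment, so the ratio would move towards 1.

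**Conclusion.** The point holds as a loss of precision in the continuous-outcome models. For HbA1c with two complete visits and equal SDs, baseline adjustment cuts the SE by about 13% to 5% at rho 0.5 to 0.8, as if 83 to 69 participants had been enrolled instead of 62. A similar gain applies with three visits. These figures depend on assumed correlations, since the documents give no correlation or SD, and the HbA1c gain could be close to nil if the baseline value itself is range-restricted. For BMI the two analyses are practically the same. No size can be given for caloric intake or physical activity. The change is worth making because it uses data already collected at negligible cost, not because the planned analysis is wrong.

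**What to change.** In the SAP, define the primary comparison for each continuous outcome as the between-arm difference at the 3-month follow-up, adjusted for the participant's own baseline value of that outcome. There are two ways to do it:
- Model post-baseline values with the baseline value as a covariate. This also works for GAMs.
- Fit a constrained longitudinal LME with a common baseline mean, with time zero defined as each participant's own baseline assessment.

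Name one in advance, since they differ when data are missing. State the assumed correlation, and say whether the 1-year HbA1c value enters the model. Reconcile protocol sections 2a and 8m on HbA1c at post-test.

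The cost is a few sentences, no new data and one estimated coefficient, which adds about 1% to the variance at most for BMI.

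### The SAP tests T2D onset and its mediation through body fat as Aims 1 and 2; neither is a protocol aim, and 62 participants cannot support inference on onset

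*SAP*

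**What the plan says.** Protocol section 1b (Objectives) sets two aims. Aim 1 is "significantly greater reductions in BMI and HbA1c, the primary outcomes, by 3-month follow-up". Aim 2 is "greater reductions in self-reported caloric intake and greater increases in physical activity by 3-month follow-up". The same section calls the study a pilot and feasibility trial and places T2D onset in the next one: "we plan on conducting a fully-power trial that will test whether this brief, cost effective prevention program significantly reduces future onset of T2D".

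The SAP (Analyses) has three parts:

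- Mixed or additive models: "For the continuous response variables in Aims 1 and 2 we will fit linear mixed effects models (LME"), or GAMs if change is nonlinear. No outcome is named.
- A survival analysis: "To detect for differences in the onset of T2D (Aim 1) between the intervention and control condition, we will fit a Cox" model, with stratified models as the fallback if hazards are not proportional.
- A mediation analysis labelled Aim 2, which involves "modeling the onset of T2D via a parametric survival regression model that includes condition and the proposed mediator (percent body fat"). It takes its mediator model from "the percent body fat model from Aim 1".

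Protocol section 2a has body fat measured by Bod Pod, but neither aim lists it. Section 8a expects 62 participants. Sections 2a and 8m propose collecting HbA1c over one year from the medical record, results sent in by participants, or a home kit.

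**The concern.** The two documents attach the same aim numbers to different questions. T2D onset, mediation and percent body fat appear in the SAP as aim-level analyses and in no protocol aim. BMI, HbA1c, caloric intake and physical activity make up the protocol's aims and are not mentioned in the SAP. Because Aim 1 is the aim that carries the primary outcomes, a reader of the SAP alone could take onset for a primary test.

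Two things are at stake. First, the report could carry an aim-level claim, or a misleading null result, on an endpoint that the protocol defers to another trial. Second, the onset hazard ratio and the proportion mediated would be very imprecise, and the hazard ratio may have no finite estimate.

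**Working it through.** **Step 1: the aims side by side.**

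| | Protocol 1b | SAP |
|---|---|---|
| Aim 1 | BMI, HbA1c | unnamed continuous variables; Cox model of T2D onset; a percent body fat model |
| Aim 2 | caloric intake, physical activity | unnamed continuous variables; mediation of T2D onset through percent body fat |
| T2D onset | left to a later trial | tested in this trial |

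This mismatch needs no assumption.

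**Step 2: is the onset analysis specified?** Neither document defines onset, its event time or a censoring rule. Onset can be seen only at a blood test, so event times are interval-censored and bunched around visits, which a standard Cox model does not handle. Protocol section 2a excludes blood tests at post-test while section 8m lists HbA1c there; these must be reconciled. The stratified fallback names no stratifier.

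**Step 3: events needed.** The documents contain no power calculation, event target or onset rate, so there is no planned figure to reproduce. The only effect size is that the parent programme "has produced a 42% to 53% reduction in future onset of overweight/obesity" (section 1a). Borrowed as an assumption, this gives HR 0.58 to 0.47. For 80% power at two-sided 0.05 with 1:1 allocation:

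events = 4 × (1.96 + 0.842)² / (ln HR)²

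- HR 0.58: 4 × 7.85 / 0.545² = 105.8, so 106
- HR 0.47: 4 × 7.85 / 0.755² = 55.1, so 56

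If all 62 participants developed T2D, power would be 57% at HR 0.58 and 84% at HR 0.47. That ceiling needs no incidence assumption.

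**Step 4: events expected.** Assumptions: 31 per arm, HR 0.5 (between the two borrowed values), no dropout, and annual control-arm risk r of 5%, 15% or 30%. With t in years, the cumulative risks are pc = 1 − (1 − r)^t for control and pt = 1 − (1 − r)^(0.5t) for Project Health. Expected events are 31 × (pc + pt). I take t = 4.5/12 (six weeks plus three months, counting follow-up from post-test) and t = 1. For example, at r = 15% and t = 1, pc = 0.150 and pt = 0.078, giving 31 × 0.228 = 7.07 events.

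Schoenfeld power (two-sided) is Φ(|ln HR|√d/2 − 1.96) + Φ(−|ln HR|√d/2 − 1.96), where d is the expected number of events. At so few events it is only indicative, so Fisher's exact test on the counts, enumerated over 31 versus 31, is shown beside it. The chance that at least one arm has no event is 1 − [1 − (1 − pc)^31] × [1 − (1 − pt)^31].

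| Time | r | Expected events | Schoenfeld power | Fisher power | At least one arm with no event |
|---|---|---|---|---|---|
| 4.5 months | 5% | 0.89 | 6.2% | <0.1% | 88% |
| 4.5 months | 15% | 2.76 | 8.9% | 0.4% | 48% |
| 4.5 months | 30% | 5.89 | 13.4% | 3.6% | 14% |
| 1 year | 5% | 2.33 | 8.3% | 0.2% | 56% |
| 1 year | 15% | 7.07 | 15.2% | 5.3% | 9% |
| 1 year | 30% | 14.36 | 26.0% | 16.7% | 0.4% |

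**Step 5: precision.** With SE(ln HR) ≈ 2/√d, seven events give a 95% interval of about exp(1.96 × 2/√7.07) = 4.4-fold either side of the estimate. The mediation adds percent body fat to a survival model fitted to the same few events, so the proportion mediated would be less stable still.

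**The case against.** Several points can be made for the SAP.

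- **The protocol's outcomes are covered by reference.** The mixed-model paragraph refers to the continuous variables of Aims 1 and 2, and the protocol says what those are. This stands: an analysis for BMI and HbA1c exists, although the SAP leaves them unnamed while it names onset.
- **The protocol is not silent on onset.** Section 1a says the programme was adapted to prevent T2D, and the one-year HbA1c collection gives the onset analysis a data source. Also true, but it does not make onset an aim, and section 1b defers that question explicitly.
- **The effect size and incidence are assumed.** The borrowed reduction concerns overweight/obesity onset. Section 3a describes the 53% figure as a 3-year result in adolescent girls and young women against assessment-only controls, which is far from adults with prediabetes and an education control. The exact percentages should therefore be read loosely. The conclusion still holds across the whole 5-30% range, and dropout would worsen it.
- **An arm with no events does not remove all information.** A one-sided likelihood bound and a log-rank test remain. This stands: the last column of the table is the chance of no finite hazard ratio estimate. Both arms are empty in 41%, 6% and 0.2% of cases at 4.5 months for r = 5%, 15% and 30%, and in at most 9% at one year.
- **Low power is acceptable in a pilot.** Agreed. The defect is presenting these models as tests of the trial's aims.

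**Conclusion.** The concern holds. The contradiction between the SAP's aims and those in protocol section 1b is textual, and no other part of either document resolves it. The claim that onset is nearly uninformative rests on an assumed control-arm risk, a borrowed hazard ratio, equal arms and full follow-up. Under those assumptions 2 to 14 events are expected by one year, against the 56 to 106 needed, and power does not exceed 26%. At 4.5 months, close to when the protocol's aims are assessed, it does not exceed about 13%. This should be corrected before outcome data are analysed, because the SAP as written makes a deferred endpoint look like an aim of this trial.

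**What to change.** Rewrite the SAP's Aims 1 and 2 to match protocol section 1b:

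1. Name BMI and HbA1c as the primary outcomes, and caloric intake and physical activity under Aim 2, as the variables for the LME/GAM analysis.
2. Remove the aim labels from the onset Cox model and the mediation. Drop both, or label them exploratory. If the Cox model stays, name the stratifier for its fallback.
3. State a definition of T2D onset and report it descriptively, as counts per arm with exact confidence intervals.
4. If percent body fat is analysed, list it as a secondary outcome.
5. Reconcile protocol sections 2a and 8m on whether HbA1c is taken at post-test.

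The SAP changes are wording only and need no new data; item 5 is a protocol clarification. The cost is that this pilot makes no inferential claim about T2D onset, a claim that its size could not support.

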8. PARTICIPANT POPULATION

a. Planned Enrollment

- (i) All subjects will be enrolled at Stanford. We expect to enroll 62 participants.
- (ii) N/A
- (iii) Participants are overweight adults (BMI between 25 and 40 kg/m²) between 18-65 years old who have been diagnosed with prediabetes, defined as having elevated HbA1c (5.7-

6.4%). As this is the first test of an adapted Project Health for individuals with Type 2 Diabetes, recruiting a sample that will most likely benefit from it is important in testing its effectiveness.

b. Age, Gender, and Ethnic Background

All participants will be 18-65 year-olds. All ethnicities and genders will be recruited and included.

c. Vulnerable Populations

This study will only enroll adults. All individuals will be consenting on behalf of themselves. We are not specifically recruiting from vulnerable populations, although as long as they meet eligibility criteria then they will be able to participate in the study. We are not specifically recruiting students or employees, but if they are interested in participating, they will not be excluded. The consent form notes the voluntary nature of their participation and that they will not lose any benefit or medical care that they are otherwise entitled for withdrawing from the study.

d. Rationale for Exclusion of Certain Populations

Children are not included as Type 2 Diabetes is not common among children.

e. Stanford Populations

Stanford students, employees, and laboratory personnel may be eligible to participate in this research study. We cannot estimate how many that might be. If any such participants are enrolled, they will go through the informed consent process as any other participant would and receive payment for their participation.

f. Healthy Volunteers

N/A

g. Recruitment Details

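### The SAP's only fallback for non-proportional hazards in the T2D onset analysis, a stratified Cox model, does not deliver the between-arm comparison

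*SAP*

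**What the plan says.** The second paragraph of the SAP's Analyses section covers T2D onset. Its purpose is to look for "differences in the onset of T2D (Aim 1) between the intervention and control condition", and for this "we will fit a Cox proportional hazard model using the survival package". Proportionality is to be assessed, and "in the event of violations of this assumption, stratified proportional hazard models will be fit". The SAP gives no model formula, covariate list, stratification variable, or test or threshold for judging a violation.

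Three other places bear on how the fallback can be read:

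- **SAP, first paragraph.** "All models will include an interaction of time since the start of the study (in months) and condition". This sentence sits in the paragraph on continuous responses, which are modelled by linear mixed effects or generalized additive models. It is not in the Cox paragraph.
- **SAP, third paragraph.** The Aim 2 mediation analysis uses a parametric survival model for onset that contains condition and percent body fat. It is not presented as a substitute for the Cox comparison.
- **Protocol section 2a, Randomization.** "We will use a random number generator to determine if participants will be in Project Health or the educational control". Allocation is simple, with equal probability and no stratification factor, so the design supplies no stratification variable either.

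Protocol section 1b names BMI and HbA1c as the primary outcomes and leaves prevention of onset to a later, fully powered trial. The SAP nevertheless files the onset comparison under Aim 1.

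**The concern.** Stratifying a Cox model deals with non-proportionality by giving each level of the offending variable its own baseline hazard. That works for a nuisance covariate whose effect nobody needs to estimate. It does not work for the treatment variable, because the treatment effect is then absorbed into the separate baselines. Here condition is the only variable the SAP associates with the model, so it is the natural variable for the assumption to fail on.

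A changing effect is not far-fetched. The program lasts six weeks, A1c is to be collected over one year, and protocol section 2g itself allows that effects may fade. If hazards were judged non-proportional, the analyst would follow the SAP to a model with no usable comparison of the arms. A replacement would then have to be chosen after seeing the data, which prespecification is meant to prevent.

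**Working it through.** The documents give no event count, hazard ratio, power or alpha for onset, so there is no planned figure to reproduce. The check is structural, followed by a numerical illustration.

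**1. Inputs.** Covariate identified: condition, x = 0 or 1 (SAP, Analyses, second paragraph). Stratification variable: none named (same place). Randomization strata: none (protocol section 2a). Sample size, for the illustration only: "We expect to enroll 62 participants" (protocol section 8a).

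**2. Stratify on condition.** The partial likelihood is a product over events i:

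L(β) = Π exp(βx_i) / Σ_{j in R_i} exp(βx_j),

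where R_i is the risk set within the stratum of participant i. If the strata are the two conditions, x_j = x_i for everyone in R_i. Each factor becomes exp(βx_i) / [n_i exp(βx_i)] = 1/n_i, where n_i is the size of R_i. Nothing depends on β. The score, Σ(x_i − mean of x in R_i), is 0. The information, Σ(variance of x in R_i), is also 0. The condition effect cannot be estimated or tested.

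**3. Stratify on another variable.** Condition now varies within risk sets, so β is estimable. The model still holds the condition hazard ratio constant over time within each stratum, so a violation arising from condition is carried through unchanged.

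**4. Numerical illustration.** One simulated data set: 62 participants, 31 per arm, censored at 12 months. Onset times are Weibull, with shape 1 and scale 30 months in control and shape 2 and scale 40 months in intervention. The different shapes make the hazards non-proportional. All these parameters are assumptions chosen to show the mechanism. The data set had 14 events.

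| Model | Result for condition |
|---|---|
| Cox, unstratified | log HR −1.03 (SE 0.59) |
| Cox, stratified on condition | log partial likelihood −46.247 at β = −2, −1, 0, 1 and 2; score 0, information 0 |
| Cox, stratified on an unrelated binary variable | log HR −1.00 (SE 0.59) |

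The second row is the flat likelihood of step 2. The third row is step 3: the estimate barely moves from the unstratified one and rests on the same proportionality assumption.

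**5. Likely amount of data.** The documents give no onset rate. If 5% to 15% of participants developed T2D, the expected number of events would be 62 × 0.05 = 3.1 to 62 × 0.15 = 9.3. For a difference in cumulative onset with the same proportion p in both arms of 31, a rough normal half-width is 1.96 × √[2p(1 − p)/31]:

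- p = 0.05: 1.96 × √(0.095/31) = 1.96 × 0.0554 = 0.109
- p = 0.15: 1.96 × √(0.255/31) = 1.96 × 0.0907 = 0.178

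That is about ±11 to ±18 percentage points. The normal approximation is poor at these counts, and an exact interval would usually be wider.

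**The case against.** The strongest reply is that the SAP never says to stratify on condition. A reader might infer that it does, and hence that the rule as written produces a wrong result. The text does not go that far. It leaves the variable open, and its one-sentence description names a comparison, not a closed covariate list. This part of the objection stands. It does not rescue the rule, because the other reading fails too: stratifying on something else leaves non-proportionality of condition untouched.

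A second reply is that the analyst could split follow-up into intervals and estimate a hazard ratio in each. That is a recognised method, but condition-by-interval terms do the work. Stratifying by follow-up interval alone leaves every risk set as it was. The SAP mentions neither intervals nor such terms for the Cox model.

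A third reply is that other information on the condition effect remains, and this is correct. A reader might infer that the fallback loses everything. However, arm-specific onset curves could still be drawn, and the mediation analysis involves a total effect of condition on onset. What is missing is a prespecified contrast on those curves, or any statement that the mediation model stands in for the onset comparison.

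Finally, the consequence is limited. The primary outcomes, BMI and HbA1c, use other models and are unaffected. If the Cox analysis were dropped as unsuited to a pilot of this size, the sentence would go with it. That is true, but the sentence is in the current SAP.

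**Conclusion.** The point holds. The one stated response to non-proportional hazards either eliminates the condition effect or leaves its non-proportionality unaddressed, so it does not deliver the between-arm onset comparison. This follows from the form of the partial likelihood and needs no assumption about event rates. It does rest on reading condition as the only term in the model, which is all the SAP identifies.

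The size is modest. The problem arises only if the assumption is judged violated, and onset is not a named primary outcome. Two further inferences should be avoided:

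- **How often the fallback would be used.** A reader might assume a 5% test and a trigger in about 1 trial in 20. The SAP specifies no test or level, and with perhaps 3 to 9 events (on the assumed 5% to 15% onset) such a test would behave poorly.
- **When onset can be seen.** A reader might suppose that onset is detectable only at the 3-month and 1-year A1c measurements. Protocol sections 2a and 8m allow the later value to come from Epic, from recent results supplied by the participant, or from a home kit, so its date is not fixed. The two sections also disagree on whether HbA1c is measured at post-test, and should be reconciled.

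**What to change.** Delete the stratified-model sentence and replace it with text along these lines:

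> In any Cox model for T2D onset, condition is kept as a covariate and is never used as a stratification variable. Whatever any check of proportional hazards shows, the difference between conditions in cumulative T2D onset by the 1-year A1c assessment is reported with an exact or small-sample 95% confidence interval. The same difference at the 3-month follow-up is secondary.

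The comparison should not depend on the outcome of a proportionality test. A data-driven switch with no stated threshold would repeat part of the present problem.

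Define the 1-year window: which dates count, which source takes precedence when more than one A1c value is available, and how participants with no result in the window are handled. The definition of T2D onset should be stated in the same place, since the documents do not give one.

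The cost is a short SAP edit, using A1c data the protocol already plans to collect. The downsides are a wide interval when events are few, and a fixed-time difference that makes no use of exact onset timing.
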